5.6. Post-discontinuation Therapy

The numbers and percentages of patients reporting post-discontinuation therapies will be provided overall, by type of therapy (surgery, radiotherapy, or systemic therapy), and by drug name.

5.7. Efficacy Analysis

Efficacy assessments are not applicable in this study. However, the investigator is required to confirm that the patient is still deriving benefit from study treatment and has no evidence of disease progression.

5.8. Analysis Related to Primary Objective

The primary objective of the study includes the evaluation of the following endpoints over the first 3 cycles (primary outcome phase):

- Incidence of severe diarrhea (\geq Grade 3)
- Incidence of prolonged Grade 2 diarrhea (defined as >7 days duration)
- Dose reductions due to diarrhea
- Dose interruptions due to diarrhea
- Treatment discontinuations due to diarrhea
- Utilization of antidiarrheals

Analyses for each of these endpoints related to the primary objective will be summarized by treatment arm using safety analysis set population. For descriptive purpose, the odds ratios with 95% confidence intervals along with exact p-value using Fisher's Exact test will be produced for comparing arms with each other. In addition, incidence of severe diarrhea (\geq Grade 3) and incidence of prolonged Grade 2 diarrhea (defined as >7 days duration) will be combined into one endpoint. Dose reductions due to diarrhea, Dose interruptions due to diarrhea and Treatment discontinuations due to diarrhea will be combined into another combined endpoint. These two

combined endpoints will be summarized and analyzed using the same approach mentioned above.

The analyses for each of the endpoints related to the primary objective will be repeated using per-protocol analysis set population as a sensitivity analysis.

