3.1. Study Rationale

Abemaciclib is an oral, selective, and potent adenosine triphosphate (ATP)-competitive inhibitor of cyclin-dependent kinases 4 and 6 (CDK4 and CDK6, respectively). It is currently approved for use in certain geographies as a monotherapy or in combination with hormone therapy for the treatment of patients with advanced or metastatic hormone receptor-positive (HR+), human epidermal growth factor receptor 2-negative (HER2-) breast cancer.

MONARCH 1, a single-arm Phase 2 study of abemaciclib 200 mg twice daily (BID) as a single agent in patients with refractory HR+, HER2- metastatic breast cancer (mBC), demonstrated that continuous dosing of single-agent abemaciclib was well tolerated and exhibited promising clinical activity (objective response rate [ORR] of 19.7% (95% confidence interval [CI] 13.3-27.5; 15% not excluded). The most common treatment-emergent adverse events (TEAEs) of any grade were diarrhea (90.2%), fatigue (65.2%), and nausea (64.4%).

MONARCH 2 was a randomized, double-blind Phase 3 study of abemaciclib in combination with fulvestrant in women with HR+, HER2- mBC who had progressed while receiving endocrine therapy. It demonstrated that abemaciclib 150 mg BID plus fulvestrant was effective, with significantly improved progression-free survival (PFS; median 16.4 versus 9.3 months; HR=0.553; 95% CI 0.449, 0.681) and in patients with measurable disease an ORR of 48.1% (95% CI 42.6,53.6) compared with 21.3% (95% CI 15.1, 27.6) in the control arm. The most common TEAEs in the abemaciclib versus placebo arms were diarrhea (86.4% versus 24.7%), neutropenia (46.0% versus 4.0%), nausea (45.1% versus 22.9%), and fatigue (39.9% versus 26.9%).

MONARCH 3 was a randomized, double-blind Phase 3 study of abemaciclib in combination with an aromatase inhibitor as initial therapy in women with HR+, HER2- mBC. It demonstrated that abemaciclib 150 mg BID plus a nonsteroidal aromatase inhibitor (NSAI) was effective as initial therapy, significantly improving PFS (median 28.18 versus 14.76 months; HR=0.540; 95% CI 0.418, 0.698); p=.000002). In patients with measurable disease, the ORR was 61% in the abemaciclib arm compared to 45.5% in the placebo arm (p=.003). The most common TEAEs in the abemaciclib versus placebo arms were diarrhea (82.3% versus 32.2%), neutropenia (43.7% versus 32.3%), fatigue (41.3% versus 33.5%), and nausea (41.3% versus 20.5%).

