Diarrhea is a frequently associated adverse event (AE) with abemaciclib and has been reported in MONARCH 1, MONARCH 2, and MONARCH 3 studies (Verzenio® United States Package Insert [USPI]; [Table JPCP.3.1](#)).

Table JPCP.3.1. Incidence of Diarrhea

[figure not shown]
Study	Patients N	All Grades (%)	Grade 3 (%)	Grade 4 (%)
MONARCH 1 200 mg PO BID monotherapy	132	90	20	0
MONARCH 2 150 mg PO BID with fulvestrant	441	86	13	0
MONARCH 3 150 mg PO BID with aromatase inhibitor	327	81	9	0

Abbreviations: BID = twice daily; PO = orally.

Diarrhea incidence was greatest during the first month of abemaciclib dosing. In MONARCH 3, the median time to onset of the first diarrhea event was 8 days and the median duration of diarrhea for Grades 2 and 3 were 11 and 8 days, respectively. In MONARCH 2, the median time to onset of the first diarrhea event was 6 days and the median duration of diarrhea for Grades 2 and 3 were 9 days and 6 days, respectively. In MONARCH 1, the median time to onset of the first diarrhea event was 7 days and the median duration of diarrhea for Grades 2 and 3 were 7.5 and 4.5 days, respectively.

In MONARCH 3, 19% of patients with diarrhea required a dose omission and 17% required a dose reduction. In MONARCH 2, 22% of patients with diarrhea required a dose omission and 22% required a dose reduction. In MONARCH 1, 26% of patients with diarrhea required a dose omission and 23% required a dose reduction. The time to onset and resolution for diarrhea were similar across MONARCH 1, MONARCH 2, and MONARCH 3 studies.

Diarrhea typically occurs within the first month of treatment and the incidence decreases over the duration of treatment. It is predictable and manageable with over-the-counter medications. The supportive diarrhea management guidelines (Sections 7.2.1 and 7.7.1) incorporated in the MONARCH study protocols, including early use of antidiarrheal agents and dose adjustments, appeared to have been effective in limiting the recurrence, duration, and severity of diarrhea. The majority of diarrhea events recovered or resolved and the rate of discontinuation due to diarrhea was low. In MONARCH 1 (Figure JPCP.3.1), the incidence of diarrhea reduced by end of Cycle 3, with no Grade 3 and 10.6% Grade 2 events.

Source: fgdiav11_90day.pdf.

Figure JPCP.3.1. Analysis of treatment-emergent adverse event of diarrhea in MONARCH 1.

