7.1. Treatments Administered

Abemaciclib monotherapy will be administered 200 mg PO BID with specific administration conditions. Patients will be instructed to take their daily doses of abemaciclib either with a meal, without a meal in a modified fasting state (defined as at least 1 hour prior to or 2 hours after a meal), or without regard to food for the first 3 cycles. Patients will be requested to record the abemaciclib dosing and administration conditions followed in a diary. Abemaciclib will be taken on Days 1 to 28 of a 28-day cycle for each treatment arm. [Table JPCP.7.1](#) shows the treatment regimens.

Patients will be instructed to commence loperamide at the first sign of loose stools and thereafter as per local label. See [Section 7.7.1.1](#) for supportive management guidance. Patients will be required to record loperamide dose and frequency in a diary. Loperamide will be supplied or reimbursed by the sponsor according to local laws. If additional antidiarrheals are prescribed by the physician, they should be entered on the concomitant medication CRF.

Table JPCP.7.1. Treatment Administration

Study Arm	Drug	Dose, mg	Route of Administration	Dose Frequency	Administration Conditions
1	Abemaciclib	200	Oral	BID	Take with a meal
2	Abemaciclib	200	Oral	BID	Take without a meal; at least 1 hour before or 2 hours after a meal (modified fasted condition)
3	Abemaciclib	200	Oral	BID	Take without regard to food

Abbreviation: BID = twice a day.

The investigator or his/her designee is responsible for the following:

- explaining the correct use of the drug and planned duration of each individual's treatment to the patient/study-site personnel/legal representative.
- verifying that instructions are followed properly the first 3 cycles. Abemaciclib is taken as per the assigned study arm outlined in [Table JPCP.7.1](#).
- maintaining accurate records of abemaciclib dispensing and collection.
- returning all unused medication to Lilly, or its designee at the end of the study, unless the site is authorized by Lilly or its designee to destroy unused medication, as allowed by local law.
- educating the patient on the management of diarrhea as per [Section 7.7.1.1](#).

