7.2. Method of Treatment Assignment

Patients who meet all criteria for enrollment will be randomly assigned to 1 of the 3 treatment arms. Assignment to treatment arms will be determined by a computer-generated random sequence using an interactive Web-response system (IWRS). Randomization will be stratified by region.

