5.1. Sample Size Determination

The primary objective of this study is to evaluate the impact of 3 different meal settings on the incidence of severe diarrhea (\geq Grade 3) or prolonged Grade 2 diarrhea (>7 days duration) as well as dose reductions, dose interruptions, and treatment discontinuations due to diarrhea, and utilization of antidiarrheals for patients receiving abemaciclib monotherapy. This study will enroll up to approximately 100 patients to obtain approximately 20 patients who complete the primary outcome phase per meal administration condition. Randomization will be 1:1:1 to the 3 administration conditions and randomization will be stratified by region. The region is defined as: AMERIT (Russia, Ukraine, Turkey) vs Non-AMERIT (Belgium, Spain, Australia). The sample size is based on regulatory guidance, not statistical powering.

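### SAP 5.8 compares arms only by crude odds ratios, which would often be 0, infinite or undefined for discontinuation due to diarrhea if its rate is 5% or less; a region-stratified risk difference would stay defined

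*SAP*

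**What the plan says.** SAP 5.8 lists six endpoints over the first three cycles: severe diarrhea, prolonged Grade 2 diarrhea, dose reductions, dose interruptions and treatment discontinuations due to diarrhea, and antidiarrheal use. Each is summarized by arm in the safety set. Arms are then compared with each other: "For descriptive purpose, the odds ratios with 95% confidence intervals along with exact p-value using" Fisher's exact test. Two composites are handled in the same way. One joins severe and prolonged Grade 2 diarrhea. In the other, dose reductions, interruptions and "Treatment discontinuations due to diarrhea will be combined into another combined endpoint". The endpoint analyses are repeated in the per-protocol set. The section names no stratum, risk difference, interval method or rule for zero cells.

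On the design, Protocol 7.2 states: "Randomization will be stratified by region". SAP 5.1 gives region two levels, AMERIT and Non-AMERIT. After that, the SAP uses region only in the demographic summary (SAP 5.4.1).

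On likely rates, Protocol 3.1 says of the MONARCH studies that "the rate of discontinuation due to diarrhea was low", with no figure. It also says: "In MONARCH 1, 26% of patients with diarrhea required a dose omission and 23% required a dose reduction". Its Table JPCP.3.1 gives 20% Grade 3 diarrhea in MONARCH 1, and the text gives 90.2% any-grade diarrhea. On antidiarrheals, Protocol 7.1 says: "Patients will be instructed to commence loperamide at the first sign of loose stools".

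Protocol 10.3 plans no hypothesis tests, calls the analysis descriptive, and asks for estimates with 95% intervals where relevant.

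**The concern.** An odds ratio has no finite non-zero value when one arm has no events, and no value at all when neither arm has any. With 20 to 33 patients per arm and a rare event, such tables are the usual result. For discontinuation due to diarrhea, the only planned between-arm estimate may then print as 0, infinity or not estimable, with at most a one-sided exact interval. Because no tests are planned, estimates and intervals carry the between-arm message. A table with no events in either arm would say nothing about how large a difference the data still allow.

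Separately, the trial randomizes within region but the comparison ignores region. SAP 5.8 does not use the word unstratified. The reading rests on the absence of any named stratum and on Fisher's test working on a single 2x2 table.

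**Working it through.** **Inputs.** SAP 5.1 wants about 20 completers per arm from up to about 100 enrolled. The plan's own arithmetic agrees: 3 x 20 = 60 evaluable. There is no power calculation to reproduce. The safety set includes all treated patients, so an arm holds between 20 and 100/3, about 33. The per-protocol set can be no larger. Rates of discontinuation (1-10%), of antidiarrheal use (80-90%) and by region are assumptions, because the documents give none.

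**Zero cells.** With a common rate p and n per arm, the chance that an arm has no events is q = (1-p)^n. A pairwise odds ratio is undefined with probability q^2, is 0 or infinite with probability 2q(1-q), and is one or the other with probability 1-(1-q)^2. At least one of the three pairs is affected with probability 1-(1-q)^3.

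| Assumed discontinuation rate | Given pair, n=20 | Given pair, n=33 | Any of 3 pairs, n=20 | Any of 3 pairs, n=33 |
|---|---|---|---|---|
| 1% | 96.7% | 92.0% | 99.4% | 97.8% |
| 3% | 79.2% | 59.8% | 90.5% | 74.5% |
| 5% | 58.8% | 33.4% | 73.6% | 45.7% |
| 10% | 22.8% | 6.1% | 32.2% | 9.0% |

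Example: p = 0.05 and n = 20 give q = 0.95^20 = 0.358, and 1-(0.642)^2 = 0.588.

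**Other endpoints, if MONARCH 1 rates carry over to three cycles.** Reductions: 0.902 x 23% = 20.7% of all patients. Interruptions: 0.902 x 26% = 23.5%.

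| Endpoint | Rate | Given pair, n=20 | Given pair, n=33 |
|---|---|---|---|
| Severe diarrhea | 20% | 2.3% | 0.13% |
| Dose reduction | 20.7% | 1.9% | 0.09% |
| Dose interruption | 23.5% | 1.0% | 0.03% |
| Dose-modification composite | 25% (assumed) | 0.6% | 0.02% |

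The severe-or-prolonged composite cannot have an empty arm unless severe diarrhea does, so its chance of one is no higher. Prolonged Grade 2 diarrhea on its own cannot be placed, because no rate is given.

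For antidiarrheal use, the failure is an arm in which every patient is a user. With z = p^n, the chance for a pair is 1-(1-z)^2. At 80%, 85% and 90% use this is 2.3%, 7.6% and 22.8% with 20 per arm, and 0.1%, 0.9% and 6.1% with 33.

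**What a risk difference shows instead.** Intervals are Miettinen-Nurminen, in percentage points. The stratified ones use Mantel-Haenszel weights and assume the regions split each arm about evenly.

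| Events | Odds ratio | Risk difference, crude | Risk difference, stratified |
|---|---|---|---|
| 0/20 vs 0/20 | undefined | 0 (-16.5 to 16.5) | 0 (-16.8 to 16.8) |
| 0/33 vs 0/33 | undefined | 0 (-10.6 to 10.6) | 0 (-10.7 to 10.7) |
| 0/20 vs 2/20 | 0 (exact 0 to 5.28), Fisher p = 0.49 | -10.0 (-30.4 to 7.3) | -10.0 (-30.7 to 7.7), one event per region |

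**Region.** This was simulated with 20,000 trials per setting, per-arm strata of 10/10, 16/4, 17/16 and 26/7, and true differences of 0 and 20 points.

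- Regional rates 20% and 40%: the crude interval is 0.8-1.7% wider than the stratified one (0.4-0.8 points). Coverage is 95.0-95.9% crude and 94.9-95.2% stratified.
- Regional rates 10% and 50%: 4.3-8.0% wider (2.0-3.6 points). Coverage is 96.5-97.4% crude and 94.9-95.6% stratified.
- No region effect, true difference 0: the stratified interval is the wider one, by 0.2-0.5% at a 20% rate and 0.7-2.1% at rates of 1-5%.

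**Does stratifying the odds ratio help?** In a separate simulation with two equal regions at 1% and 3%, the odds ratio was 0, infinite or undefined in 88.8% of tables at 20 per arm and 75.7% at 33. The figures were the same for the crude and the Mantel-Haenszel odds ratio.

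**The case against.** The affected output is labelled descriptive, no test is planned and the size is not powered. Counts by arm are the main result and do not change; a reader who sees 0/20 against 2/20 already has the data. Protocol 10.3 asks for intervals only where relevant and allows further exploratory analyses, so a risk difference could be added without touching the SAP. Discontinuation is one of six endpoints, and the composite that contains it has a usable comparison. No passage suggests that diarrhea differs by region. Without such a difference, stratifying gains nothing and leaves about 4 to 7 patients per arm in the smaller region at an 80/20 split.

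Most of this stands, and it limits the weight of the point. It does not remove it: for a named endpoint of the primary objective, the one planned between-arm estimate may have no usable value, and an alternative that always has one costs almost nothing. Choosing that alternative in advance is better than choosing it after the zero cells are seen.

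A reader might infer that ignoring the stratum makes the comparison invalid. It does not. The crude analysis remains valid, and in these simulations its coverage was at or above 95%. A reader might also infer that antidiarrheal use is exposed as badly as discontinuation. That would need near-universal use, and the documents give no usage rate.

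**Conclusion.** The point holds as a modest improvement. For discontinuation due to diarrhea, a given pairwise odds ratio is 0, infinite or undefined in 59-97% of tables at 20 per arm and 33-92% at 33, provided the rate is 1-5%. At 10% the figures are 23% and 6%. An unqualified claim that the odds ratio often fails is therefore not supported, because the documents say only that the rate is low, and they say it of the MONARCH studies together rather than of the monotherapy study alone.

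Endpoints near 20% and the dose-modification composite are essentially unaffected, assuming MONARCH 1 rates carry over. Prolonged Grade 2 diarrhea cannot be classified either way. The unused stratum is secondary: it costs about 1-2% of interval width in a moderate case and 4-8% in an extreme one, and nothing if the regions are alike.

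**What to change.** In SAP 5.8, add for each pairwise comparison a risk difference with a Miettinen-Nurminen score 95% interval, stratified by region with Mantel-Haenszel weights. State that the unstratified version is used if a region is empty in one of the two arms, because that region's weight would then be zero and its patients would drop out of the estimate. Keep the odds ratio as supportive and say how it is displayed when it is 0, infinite or undefined. Stratifying the odds ratio alone is not a substitute, because it leaves the zero cells in place.

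The cost is a few lines of SAP text and standard code. No new data are needed, since region is already recorded for randomization. The downsides are slightly longer tables, small strata if the regions are unbalanced, and an interval up to about 2% wider when region has no effect or events are rare.

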7.7.1.1. Supportive Management for Diarrhea

Patients should receive instructions on the management of diarrhea and prescribed antidiarrheal therapy (protocol recommended loperamide) on Day 1. The antidiarrheal agent, loperamide is not for prophylactic use, and should only be used in the event of diarrhea. Loperamide will be supplied or reimbursed by the sponsor according to local laws. In the event of diarrhea, provided loperamide antidiarrheal therapy should be initiated as early as possible and the site should follow the guidance below:

- At the first sign of loose stools, the patient should initiate loperamide antidiarrheal therapy, if not already receiving such therapy, and notify the investigator/site for further instructions and appropriate follow-up.
- Patients should also be encouraged to drink fluids (for example, 8 to 10 glasses of clear liquids per day).
- Site personnel should assess response within 24 hours.
- If diarrhea does not resolve with loperamide therapy within 24 hours to either baseline or Grade 1, abemaciclib should be suspended until diarrhea is resolved to baseline or Grade 1.
- When abemaciclib recommences, dosing should be adjusted as outlined in [Table JPCP.7.2](#) and [Section 7.4.1.1](#).

In cases of significant diarrhea, Grades 2 through 4 ([Appendix 7](#)), that have not responded to interventions as outlined above, if the investigators are considering the addition of steroids to treat potential colitis, the sponsor strongly recommends an endoscopic procedure to document colitis prior to initiating steroids.

In cases of severe diarrhea, the measuring of neutrophil counts and body temperature and proactive management of diarrhea with antidiarrheal agents should be considered.

If diarrhea is severe (requiring intravenous [IV] rehydration) and/or associated with fever or severe neutropenia, broad-spectrum antibiotics such as fluoroquinolones must be prescribed.

Patients with severe diarrhea or any grade of diarrhea associated with severe nausea or vomiting should be carefully monitored and given IV fluid (IV hydration) and electrolyte replacement.

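### Antidiarrheal utilization is undefined and is reduced by the planned analysis to any-use, which is insensitive to moderate food effects and does not register how much or how long loperamide is taken

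*SAP*

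**What the plan says.** SAP 5.8 lists six endpoints for the primary objective, the last being utilization of antidiarrheals. It then sets one approach for all of them: "Analyses for each of these endpoints related to the primary objective will be summarized by treatment arm using safety analysis set population". For descriptive purposes it calls for "the odds ratios with 95% confidence intervals along with exact p-value using" Fisher's exact test, for each pair of arms. No endpoint is excepted, and neither SAP 4.1 nor Protocol 10.3.1 defines utilization.

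On loperamide, Protocol 7.1 says "Patients will be instructed to commence loperamide at the first sign of loose stools and thereafter as per local label". Protocol 7.7.1.1 adds that "loperamide is not for prophylactic use, and should only be used in the event of diarrhea". Both apply to every arm.

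On data, Protocol 7.1 says "Patients will be required to record loperamide dose and frequency in a diary". Table JPCP.2.2 has loperamide use recorded daily in the e-diary, and Table JPCP.2.1 adds about a week of baseline recording of antidiarrheal use. Antidiarrheals prescribed in addition go on the concomitant-medication CRF. The SAP plans no summary by arm of days, dose or duration of loperamide use.

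**The concern.** An odds ratio and Fisher's test need a two-category outcome, so the method turns utilization into used or not used. Loperamide is started at the first loose stool and is not given prophylactically, so any-use should follow any-grade diarrhea. The endpoint then adds little to the any-grade incidence already in the adverse-event tables. One day of loperamide and sixty days count the same.

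The protocol's rationale (3.1) is that food may alter both the incidence and the severity of diarrhea. Shorter or milder diarrhea would show in how much loperamide is taken, which is recorded but not analysed by arm. Similar any-use percentages with a large p-value could be read as showing that food makes no difference to antidiarrheal need, when the quantity that might have changed was not summarised.

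**Working it through.** **Inputs from the documents**
- Any-grade diarrhea at 200 mg BID monotherapy: 90.2% (Protocol 3.1; shown as 90% of 132 patients in Table JPCP.3.1, row "MONARCH 1 200 mg PO BID monotherapy").
- Patients per arm: 60 / 3 = 20 completers (SAP 5.1). If about 100 are enrolled, 100 / 3 ≈ 33. Protocol 5.2 and SAP 5.1 word enrollment differently, so both sizes are shown.
- Two-sided 95% intervals (Protocol 10.3), read here as a two-sided 5% level.

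**The plan's own figure.** The sample size rests on regulatory guidance, with no alpha, power or effect size. Only 3 × 20 = 60 can be checked.

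**Step 1: expected any-use.** Any-use ≈ P(any diarrhea) × P(loperamide given diarrhea). No document gives the second term. If it is 0.70 to 1.00 (assumption): 0.902 × 0.70 = 0.63 and 0.902 × 1.00 = 0.90.

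**Step 2: what Fisher's test can see.** Power = sum over all (i, j) with Fisher p ≤ 0.05 of Bin(i; n, p1) × Bin(j; n, p2), by full enumeration.

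| Any-use, two arms | 20 per arm | 33 per arm |
|---|---|---|
| 90% v 90% | 1% | 1% |
| 90% v 80% | 7% | 12% |
| 90% v 70% | 24% | 42% |
| 90% v 60% | 49% | 75% |
| 90% v 50% | 74% | 94% |

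The first row is the test's false-positive rate, not power. With 18/20 users in one arm, the other must have 11/20 or fewer for p ≤ 0.05 (p = 0.031, OR 7.4). With 30/33 it must have 22/33 or fewer (p = 0.033).

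If uptake is below 100%, the baseline is lower. With 70% to 90% uptake and any-grade diarrhea halved, any-use goes from 63% to 31.5% or from 81% to 40.5%. Power at 20 per arm is then 38% to 67%.

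**Step 3: change in amount only.** If food shortens loperamide use but the same share of patients ever take it, the any-use proportions do not move. Fisher's test then stays at about 1%, whatever the size of the reduction.

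**Step 4: days of use, illustration only.** The documents give no mean or SD. Assume 90% users in both arms, gamma-distributed days among users with a mean of 20 in one arm, and a two-sided 5% rank test, by simulation:

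| Mean days among users | CV | 20 per arm | 33 per arm |
|---|---|---|---|
| 20 v 10 | 1.2 to 0.6 | 21% to 72% | 33% to 91% |
| 20 v 14 | 1.2 to 0.6 | 9% to 28% | 12% to 41% |

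Days of use can register a change that any-use cannot, but with this sample size they are also weak for a 30% reduction.

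**The case against.** A reader might infer that the endpoint sits near 90% in every arm and cannot show a food effect. The documents do not support that.
- The 90.2% is any-grade diarrhea across MONARCH 1, with no food condition stated. It is not loperamide use over three cycles. Carrying it into every arm assumes full uptake and no food effect on any-grade incidence, which is part of what the study examines.
- A fall from 90% to 50% would be flagged 74% of the time at 20 per arm and 94% at 33.

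A single contrast such as 1% for any-use against 47% for days (20 v 10 days, CV 0.8, 20 per arm) would also mislead. It fixes any-use as equal in the two arms, so Fisher's test is scored under its own null, and it rests on one undocumented scenario.

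Power is a secondary yardstick here. Protocol 10.3 plans no hypothesis tests, the p-values are labelled descriptive, and other primary endpoints are weak too: severe diarrhea at 20% v 5% has 17% power at 20 per arm. That stands. But a descriptive study depends on its summaries being informative, and this one omits the amount of use whatever the power.

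Two practical objections also stand. Dose and frequency are documented only as going into a diary (Protocol 7.1). The e-diary text names only loperamide use (Table JPCP.2.2, Protocol 9.4.2.5), and SAP 5.5 names morning-dose, evening-dose and bowel-movement diaries but none for loperamide. And because loperamide follows the local label, total dose may differ by country for reasons unrelated to food.

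There is partial cover elsewhere: concomitant medications by arm (SAP 5.4.4), adverse-event severity by arm (SAP 5.9.2) and optional exploratory analyses (Protocol 10.3). None commits to the amount of loperamide.

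**Conclusion.** The point holds in limited form. Utilization is undefined; that it is binary is implied by the method, not written. As any-use it is expected to be high and to track any-grade diarrhea, so it is insensitive to moderate falls (7% to 24% power at 20 per arm, 12% to 42% at 33, for 90% v 80% to 70%) and blind to changes in amount or duration. It is not blind to a very large fall.

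The expected level, 63% to 90%, rests on a historical diarrhea rate and an assumed uptake. The gain from analysing days of use cannot be sized from the documents, and the figures in Step 4 are illustrative only. Confidence is medium. The change is worth making because it uses data the protocol already requires.

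**What to change.** In SAP 5.8:
1. Define utilization. Keep any-use as planned.
2. Add a descriptive by-arm summary of days with loperamide use over the first 3 cycles, per 28 observed diary days, from the daily e-diary: median, quartiles, and between-arm difference with 95% CI.
3. State that days of abemaciclib suspension stay in the denominator. Otherwise patients whose diarrhea led to suspension would lose the very days on which loperamide use is likely.
4. Show missing diary days by arm. Protocol 10.3 does not impute missing data, so the reader needs to see them.
5. Report total loperamide dose as supportive, where the diary captures dose, noting that dosing follows the local label and may vary by country. First confirm which diary holds it.
6. Take other antidiarrheals from the concomitant-medication CRF.

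This fits the descriptive plan in Protocol 10.3, which already provides for summaries of continuous variables and for intervals where relevant. The cost is SAP wording, some programming, and diary missingness becoming visible. On the documents' account it needs no new visits, data collection or change in patient management.
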